Фонд за науку
Републике Србије

Utility of plasma drug level monitoring and *CYP2C19* genotyping in dose personalization of escitalopram therapy

PsyCise_E

Principal Investigator: **Asst. [name] PhD**

Department of Physiology, Faculty of Pharmacy, University of Belgrade, Serbia

Document Date: 12th January 2022

Clinical trial protocol

Test groups:

PsyCise trial is designed to quantify changes in clinical outcomes in participants treated for depression using personalized antidepressant dosing regimen, based on therapeutic drug monitoring (TDM) and CYP2C19 genotyping; as compared to the standard, “one size fits all” dosing. In order to reach this goal, we have defined two test groups based on the TDM findings. Namely, all participants who enter the trial (Visit 0) will begin taking standard escitalopram dose of 10 mg/day for two weeks when their blood samples will be taken for the purpose of TDM, and based on their steady state escitalopram concentrations they will be allocated to one of two groups at week 4 of the trial (visit 1):

- 1) “Standard dose” group: Participants will be allocated to this group if their TDM results at week 2 show their steady state escitalopram plasma concentrations were inside “therapeutic window” (25-50 ng/ml). For these participants, initial standard escitalopram dose of 10 mg/day is estimated to be optimal so they will continue to receive the same dose until the end of the trial at week 8 (visit 2).
- 2) “Adjusted dose” group: If TDM results at week 2 suggest that participant taking standard dose is underdosed or overdosed, given participant is allocated to this group. New, personalized dosing regimen will be produced for this participants based on steady state escitalopram plasma concentrations measured at week 2, and they will receive personalized escitalopram dose from week 4 (visit 1) until the end of the trial at week 8 (visit 2).

Course of the trial:

Week 0

Initial Visit (Visit 0 – V0)

- Participant will be enrolled at this point if inclusion criteria are met.
- Escitalopram monotherapy for Major Depressive Disorder in previously untreated patient will be initiated at standard dose of 10 mg/day.
- Outcomes measured:
 1. General and socio-demographic information
 2. Clinical questionnaires
 3. Anthropometric measurements
 4. Cardiological assessment
 5. Serum samples for biochemical analyses
 6. Buffy coat samples for DNA extraction and *CYP2C19* genotyping*

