(*Sample is not time dependent, it can be taken at any visit)

Week 2

Mid-Visit (Vk)

- Escitalopram plasma concentrations reach steady state.
- Plasma sample taken for the purpose of TDM and group allocation.

- Percentages of participants who are underdosed and overdosed will be measured and used to confirm previous findings [Jukić 2018]

Week 4

Visit 1 (V1)

- Participants are allocated to the “Standard dose” or “Adjusted dose” group
- Independent clinician prescribes new dosing regimen to the participants in “Adjusted dose” group, and informs patients in “Standard dose” group to continue taking the same standard escitalopram dose.
- Clinician who usually monitors given patient is unaware of the group patient is allocated to, or the dose prescribed to a patient at Visit 1.
- Outcomes measured:
 1. Clinical questionnaires
 2. Anthropometric measurements
 3. Cardiological assessment
 4. Serum samples for biochemical analyses
 5. Plasma samples to reconfirm TDM findings in VK

Week 8

Visit 2 (V2)

- Final visit of the trial and the end of the follow-up.
- Outcomes measured:
 1. Clinical questionnaires
 2. Anthropometric measurements
 3. Cardiological assessment
 4. Serum samples for biochemical analyses
 5. Plasma samples to reconfirm TDM findings in VK and V1 for Standard dosing group, and to determine whether personalized dose is optimal for the patients in Personalized dosing group.

If needed, alternative course will be used:

Week 0

Initial visit + Mid-visit (V0+k)

- Participant on the stable (longer than 2 weeks) monotherapy of Major Depressive Disorder with standard dose of escitalopram (10 mg/day) will be enrolled if other inclusion criteria are met.
- Outcomes measured:
 1. General and socio-demographic information
 2. Clinical questionnaires
 3. Anthropometric measurements
 4. Cardiological assessment
 5. Serum samples for biochemical analyses
 6. Plasma sample for the purpose of TDM and group allocation.
 7. Buffy coat samples for DNA extraction and *CYP2C19* genotyping*

(*Sample is not time dependent, it can be taken at any visit)

Week 2

Visit 1 (V1) – *Identical to the standard protocol*

- Participants are allocated to the “Standard dosing” or “Personalized dosing” group
- Independent clinician prescribes new dosing regimen to the participants in “Personalized dosing” group, and informs patients in “Standard dosing” group to continue taking the same standard escitalopram dose.

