- Clinician who usually monitors given patient is unaware of the group patient is allocated to, or the dose prescribed to a patient at Visit 1.
- Outcomes measured:
 1. Clinical questionnaires
 2. Anthropometric measurements
 3. Cardiological assessment
 4. Serum samples for biochemical analyses
 5. Plasma samples to reconfirm TDM findings in V_k

Week 6

Visit 2 (V2) – *Identical to the standard protocol*

- Final visit of the trial and the end of the follow-up.
- Outcomes measured:
 1. Clinical questionnaires
 2. Anthropometric measurements
 3. Cardiological assessment
 4. Serum samples for biochemical analyses
 5. Plasma samples to reconfirm TDM findings in V_k and V1 for Standard dosing group, and to determine whether personalized dose is optimal for the patients in Personalized dosing group.

Hypotheses:

- 1) More than one quarter of participants will be overdosed or underdosed under standard escitalopram dosing regimen (10 mg/day), as determined by TDM data 2 weeks after the beginning of the therapy.
- 2) Participants with escitalopram steady state plasma concentration outside the therapeutic window (“Adjusted dose” group) will experience reduced efficacy and more severe side effects of escitalopram therapy before dose personalization (at V1) compared to the participants with escitalopram levels within therapeutic window (“Standard dose” group) at standard dosing.
- 3) Participants with escitalopram steady state plasma concentration outside the therapeutic window (“Adjusted dose” group) will show improved efficacy and less severe side effects of escitalopram therapy after dose personalization (at V2) as compared to before (at V1), and will reach clinical outcomes comparable to the “Standard dose” group (at V2).

- 4) Decisions on whether to use personalized or standard dosing, and how to adjust personalized dose based on TDM data could have been determined before the beginning of the treatment using predictive model which, besides other predictors also includes *CYP2C19* genotyping data.

Statistical Analysis Plan

Primary outcomes:

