2. Covariables: Test group (Personalized vs Standard dosing), Age, Sex (Male=0, Female=1), Smoking status (0=Non-smoker, 1=Smoker), Alcohol consumption (0=No, 1=Yes), Coffee consumption (0=No, 1=Yes), Use of psychoactive substances (0=No, 1=Yes), Metabolic syndrome (0=No, 1=Yes), Creatinine clearance, AST/ALT ratio.

Positive outcome: Test group is a significant factor ($\alpha=0.05$)

Secondary outcomes:

Retrospective TDM data on 2087 patients taking escitalopram [Jukić 2018] suggests that, in the clinical setting, about 40% of patients are expected to have their plasma escitalopram concentrations under the lower limit of the therapeutic window (25 ng/ml), and for about 10% of patients we expect to have plasma escitalopram levels above the upper limit of the therapeutic window (50 ng/ml). One of our aims is to try to confirm these findings using prospective study design which allows for the better control of the confounding factors compared to the retrospective data. Number of the patients with plasma escitalopram levels outside the therapeutic window under standard dosing regimen (10 mg/day) will be assessed using TDM data at Mid-Visit (VK), 2 weeks after the beginning of the therapy.

Big disadvantage of TDM guided establishment of the optimal drug exposure in the given patient is that it takes 4 weeks to personalize escitalopram dose and 2 more weeks to achieve optimal steady state drug concentrations. Alternative approach would be to build model that could predict optimal dose for every patient even before the initiation of the treatment. This model would have to include patient data on factors that could impact escitalopram exposure such as body weight, liver and kidney functions and genotype for the *CYP2C19* gene which is responsible for the interindividual variability in the rate of escitalopram metabolism in liver [Jukić 2018]. After all participants have finished the trial we will retrospectively build model using data collected during the trial, and then validate our model comparing it to the TDM method of dose personalization. For this purpose, all patients will be genotyped for *CYP2C19* gene and divided into 4 groups based on the enzymatic capacity of CYP2C19 enzyme:

1. Poor metabolizer (PM): Carries *2/*2, *2/*3 or *3/*3 *CYP2C19* genotype. Almost absent CYP2C19 enzyme activity
2. Intermediate metabolizer (IM): Carries *1/*2 or *1/*3 *CYP2C19* genotype. Reduced CYP2C19 enzyme activity

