3. Normal metabolizer (NM): Carries *1/*1 *CYP2C19* genotype. Normal CYP2C19 enzyme activity
4. Ultra rapid metabolizer: Carries *1/*17 or *17/*17 *CYP2C19* genotype. Increased CYP2C19 enzyme activity

Multiple linear regression model will be build using selected variables:

1. Dependent variable: Plasma escitalopram concentrations at Week 2 (Vk) after the initiation of the treatment
2. Independent variables: Body mass index, PM status (0=Yes, 1=No), IM status (0=Yes, 1=No), NM status (0=Yes, 1=No), UM status (0=Yes, 1=No), Creatinine clearance, AST/ALT ratio

Other outcome measures/observations:

To further validate our primary outcome measures: escitalopram treatment efficacy and severity of adverse effects, we will use Clinical Global Impression (CGI) scales. Scores will be determined for all 3 CGI scales: for Severity of illness (CGI-S) scale at baseline, visit 1 and visit 2, and for Global improvement (CGI-I) scale and for Efficacy Index (CGI-E) at visits 1 and 2. Differences in all 3 CGI scales between visits 1 and 2 will be compared between test groups separately using ANCOVA tests with the equivalent sets of covariates to the ones used for HAM-D scale.

In all patients at baseline and at visits 1 and 2, electrocardiography will be performed in order to monitor potential QT interval prolongation. We will test for correlation between QT interval length and escitalopram plasma levels at various visits, and also we will compare changes in QT interval length between visit 1 and visit 2 in both test groups using mixed ANCOVA test adjusting for the baseline QT length.

Due to high comorbidity of anxiety and depression, and since escitalopram is frequently prescribed in anxiety disorders, we will explore severity of anxiety symptoms in all participants at baseline (V0), Week 4 (V1) and Week 8 (V2) of the treatment by using clinician reported Hamilton anxiety rating scale (HAM-A). Severity of anxiety symptoms will be compared between two test groups at two time points (V1 and V2) using mixed analysis of covariance (Mixed ANCOVA). Variables to be considered as covariates will be: Baseline HAM-A score (V0), Childhood trauma questionnaire score at V0, Age, Sex (Male=0, Female=1), Smoking status (0=Non-smoker, 1=Smoker), Alcohol consumption (0=No, 1=Yes), Metabolic syndrome (0=No, Yes).

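### The hypothesis 4 model is validated only against the TDM decision from one allocation sample; the V1 and V2 concentrations, which could test both methods, have no role

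*Combined protocol and SAP*

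**What the plan says.** Hypothesis 4 has two parts: whether to personalize, and "how to adjust personalized dose based on TDM data could have been determined before the beginning of the treatment". Both are to be settled by a pre-treatment model that includes *CYP2C19* genotype. The Secondary outcomes section of the SAP describes the aim as predicting each patient's best dose before treatment starts.

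- **Building the model.** After the last participant finishes, "we will retrospectively build model using data collected during the trial". It is a multiple linear regression whose dependent variable is "Plasma escitalopram concentrations at Week 2 (Vk) after the initiation of the treatment".
- **Validating the model.** The only reference named is TDM: the investigators will "validate our model comparing it to the TDM method of dose personalization". No agreement measure, success threshold, data split or resampling is given.
- **Where the TDM decision comes from.** Under Test groups, the personalized regimen is "based on steady state escitalopram plasma concentrations measured at week 2". In the alternative course, the allocation sample is taken at enrolment instead, after more than two weeks on 10 mg/day.
- **Other plasma samples.** The V1 sample, taken before any dose change takes effect, is meant to reconfirm the earlier TDM result. The V2 sample does the same in the standard group, and in the other group serves "to determine whether personalized dose is optimal for the patients in Personalized dosing group". Neither is assigned to the model or to its validation.

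**The concern.** One measurement serves as the model's outcome, as the basis of the TDM decision and, through that decision, as the yardstick. A single plasma sample varies around the patient's usual level. If that variation puts a patient on the wrong side of 25 or 50 ng/ml, TDM misclassifies the patient, and a model that had the usual level right is marked wrong. TDM agrees with itself by construction, so the model can at best copy it, errors included.

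The second gap is the adjusted dose. The regression predicts a concentration on 10 mg/day. Nothing in the plan compares a prediction with what was measured after the dose changed, although V2 provides that measurement.

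At stake is how the hypothesis 4 result can be read. Agreement of, say, 70% could mean a poor model, or one that classifies patients better than the single sample does. The planned comparison cannot tell these apart. It could also credit a model for reproducing TDM decisions that V2 shows to have missed the window.

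**Working it through.** The plan states no sample size, target agreement or accuracy for the model, so there is no figure of its own to reproduce. The check measures how far one sample limits the comparison.

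**Inputs from the documents.** Window 25 to 50 ng/ml (Test groups). About 40% of patients expected below it and about 10% above (Secondary outcomes). All patients on 10 mg/day up to V1.

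**Assumptions.** Concentrations are lognormal. The 40%/10% shares describe single samples. Within-patient CV, including assay error, is 10%, 20% or 30%, because the documents give none. Errors at Vk and V1 are independent.

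**Step 1: spread of single samples.** Log SD = ln(50/25) / (z0.90 − z0.40) = 0.6931 / (1.2816 + 0.2533) = 0.452, so the variance is 0.204. Median = exp(ln 25 + 0.2533 × 0.452) = 28.0 ng/ml.

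**Step 2: split of the variance.** Within-patient log variance = ln(1 + CV²). The rest is between patients. The maximum log-scale R² against one sample is between / total.

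| CV | Within | Between | Maximum R² |
|---|---|---|---|
| 10% | 0.010 | 0.194 | 0.194/0.204 = 0.95 |
| 20% | 0.039 | 0.165 | 0.165/0.204 = 0.81 |
| 30% | 0.086 | 0.118 | 0.118/0.204 = 0.58 |

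**Step 3: agreement on the three classes (below, in, above the window).** These are bivariate normal probabilities. The correlation is √R² between true exposure and one sample, and R² between two samples.

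| CV | True-exposure model v Vk class | Vk class v V1 class | Adjusted-group patients with true exposure inside the window |
|---|---|---|---|
| 10% | 90% | 86% | 11% |
| 20% | 80% | 72% | 23% |
| 30% | 70% | 59% | 38% |

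Because V1 is a sample of the same kind on the same dose, the true-exposure model would also match V1 in 90%, 80% and 70%, ahead of the Vk-based class each time. The planned comparison scores that model below TDM's automatic 100%.

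**Step 4: a less than perfect model.** Suppose the model explains half of the variance in true log exposure (an assumption). Out of sample it matches V1 in 66%, 64% and 60%, against 86%, 72% and 59% for the Vk class. TDM is clearly better at a CV of 10%, and the two are about equal at 30%. Only a comparison against V1 would show which case applies.

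**Sensitivity.** If the 40%/10% shares describe true exposure instead, the true-exposure model agrees with the Vk class in 90%, 81% and 73%, and Vk with V1 in 86%, 73% and 63%.

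The gain from using V2 was not computed, because the documents give neither a dose-adjustment algorithm nor concentrations after adjustment.

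**The case against.** **Reproducing the TDM decision is part of the hypothesis.** Hypothesis 4 asks whether the decisions "could have been determined before the beginning of the treatment using predictive model", so agreement with TDM is a legitimate measure, at least for the choice between standard and personalized dosing. This stands, and agreement with TDM should be kept. A reader might infer that hypothesis 4 goes wholly unanswered; the documents do not support that.

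**No model can fail.** A reader might also infer that even a perfect model would appear to fail. The plan has no pass rule, and 90% agreement at a CV of 10% would not look like failure. A model that reproduced Vk itself would agree completely. The ceiling applies only to a model of true exposure, and its height depends on an assumed CV.

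**The direction of bias is not established.** With no hold-out stated, the model is fitted and judged in the same patients, which pushes apparent agreement up. Random error in the dependent variable does not bias linear coefficients; it lowers R² and precision. Both points stand. In-sample optimism does not repair the yardstick, however, and resampling alone would not either.

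**The plan does not exclude V1 and V2.** True, and the TDM method could be read to include its later checks. But the regression names only the week 2 concentration, and no validation use of V1 or V2 is specified.

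**A realistic model gains little from a better reference.** For a model explaining half of true exposure, replacing Vk by the mean of Vk and V1 raises agreement by only about 1 to 5 points. This stands. The larger benefit is that TDM is scored too, on a sample that neither method has used.

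**Conclusion.** The concern holds in a limited form. As written, the validation counts TDM's sampling error against the model, cannot show the model to classify exposure as well as TDM or better, and leaves the dose-adjustment part unchecked against any concentration on the adjusted dose.

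The size depends on a within-patient CV that the documents do not give. Over 10% to 30%, agreement of a true-exposure model with the allocation class is capped at about 90% down to 70%, while the allocation class repeats at V1 in about 86% down to 59%. These figures also rest on the lognormal fit to the plan's 40%/10% shares. The R² ceilings are on the log scale, although the SAP specifies no log transform. The net direction of bias in the planned result is unknown.

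This is a secondary, retrospective analysis that affects neither allocation nor the primary outcomes. It does carry one of the four hypotheses, and the data to improve it are already scheduled, so the SAP should be changed.

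**What to change.** Change the SAP's model section as follows.

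1. **Score both methods against V1.** Keep agreement with the TDM decision and name the measure. Add a side-by-side comparison of the model's cross-validated prediction and the TDM class from the allocation sample (Vk, or the enrolment sample in the alternative course), each against the V1 concentration. Leave V1 out of the fit used here, so that it remains an independent yardstick. A model fitted to Vk and V1 together may be reported separately for precision, but should not be benchmarked against Vk-to-V1 agreement, because a two-sample mean and a single sample are not comparable references.
2. **Use V2 for the adjustment.** In the Adjusted group, calculate predicted minus observed V2 concentration on the dose actually taken, once for the model and once for the allocation concentration scaled by dose (allocation concentration × dose taken / 10 mg). Compare the two sets of errors. Do not count correct window status: a TDM-adjusted dose would presumably always be predicted to fall inside the window.

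**Cost.** Wording and extra analysis only; no new visit, sample or change in treatment. Two limits should be stated. Scaling assumes dose-proportional exposure. And V2 tests predictions only at the doses TDM chose, so the model's own dose recommendation is not tested directly.

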Other primary outcome we will use to quantify changes in clinical outcomes between test groups will be severity of the treatment side effects measured using clinician reported UKU (*Udvalg for Kliniske Undersogelser*) side effect rating scale. UKU scale rates 48 potential adverse reactions with intensity score ranging from 0 to 3 where score 3 signifies maximal intensity and score 0 signifies absence of the adverse reaction. Adverse drug reaction intensity scores for all 48 adverse reactions monitored with UKU scale will be measured at weeks 4 (V1) and 8 (V2) after the initiation of the escitalopram therapy. Due to large number of comparisons, significance measures will be adjusted using False Discovery Rate (FDR) correction. Absolute values of all 48 Adverse reaction scores will be compared between test groups and between two time points using mixed model analysis of covariance (Mixed ANCOVA) where variables will be assigned as follows:

1. Dependent variable: Adverse drug reaction score for the given adverse reaction measured by UKU scale
2. Independent variable - Fixed factor: Test group (Personalized vs Standard dosing)
3. Independent variable - Repeated measurements: Visit (Visit 1 vs Visit 2)
4. Covariables: Age, Sex (Male=0, Female=1), Smoking status (0=Non-smoker, 1=Smoker), Alcohol consumption (0=No, 1=Yes), Coffee consumption (0=No, 1=Yes), Use of psychoactive substances (0=No, 1=Yes), Metabolic syndrome (0=No, 1=Yes), Creatinine clearance, AST/ALT ratio.

Positive outcome: interaction between group and visit is significant ($\alpha=0.05$)

Alternatively, proportions of patients with intensity score greater than 0 (UKU scale intensity score >0 signifies the presence of the given adverse reaction) will be compared between the groups for all 48 adverse effect monitored with UKU scale at two time points: 4 weeks after the enrolment (V1) and 8 weeks after the enrolment (V2). Due to large number of comparisons, significance measures will be adjusted using False Discovery Rate (FDR) correction. Proportion of individuals in two test groups affected with the given adverse reaction will be compared using binary logistic regression analysis separately for visit V1 and visit V2 as follows:

1. Dependent variable: Frequency of the individuals affected with the given adverse drug reaction measured by UKU scale

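### The concentration-prediction model for Hypothesis 4 represents liver function only by the AST/ALT ratio, which discards enzyme level and cannot register a proportional rise in both enzymes

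*Combined protocol and SAP*

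**What the plan says.** Hypothesis 4 holds that the choice between standard and personalized dosing, and the size of any adjustment, could have been made ahead of therapy from a predictive model. The SAP's Secondary outcomes section says what that model has to contain: "factors that could impact escitalopram exposure such as body weight, liver and kidney functions and genotype" for *CYP2C19*.

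The same section then specifies a multiple linear regression. Its dependent variable is "Plasma escitalopram concentrations at Week 2 (Vk) after the initiation of the treatment". Its seven listed predictors are body mass index, four metabolizer-status indicators, creatinine clearance and the AST/ALT ratio; the list closes with "UM status (0=Yes, 1=No), Creatinine clearance, AST/ALT ratio". It has no AST or ALT level, multiple of the upper limit of normal, bilirubin, albumin or impairment category. The visit from which the ratio is taken is not stated.

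The course of the trial lists "Serum samples for biochemical analyses" at V0 (V0+k in the alternative course), V1 and V2, without naming the analytes. On eligibility, the initial visit says only "Participant will be enrolled at this point if inclusion criteria are met". The criteria themselves are not listed.

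**The concern.** The plan gives a reason for a hepatic predictor and then picks a variable that need not carry the information wanted. A ratio describes how two enzymes stand relative to each other and says nothing about how high either one is. If enzyme level bears on exposure, the regression cannot use it.

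Two things are at stake. The model may predict week 2 concentration less well than the collected data allow, which weakens the test of Hypothesis 4. Also, a coefficient near zero on the ratio could be reported as showing that liver function does not matter, when only the relative position of the two enzymes was examined.

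**Working it through.** The plan states no figure that can be reproduced here. The check is algebraic, followed by an illustration under assumed distributions.

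**1. Invariance of the ratio.** For any common factor k, (k × AST)/(k × ALT) = AST/ALT. With assumed enzyme values:

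| AST | ALT | Ratio |
|---|---|---|
| 20 | 20 | 1.0 |
| 200 | 200 | 1.0 |
| 20 | 10 | 2.0 |
| 50 | 100 | 0.5 |
| 150 | 75 | 2.0 |

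Rows 1 and 2 differ tenfold in level and are identical to the model. Rows 3 and 5 also share a ratio at very different levels. Rows 4 and 5 show that unequal rises do move the ratio, so the loss is not total in every case.

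**2. What the ratio imposes on the regression.** On the log scale, log(AST/ALT) = log AST − log ALT. A single coefficient b on this term fixes the coefficients at +b for log AST and −b for log ALT, so they sum to zero. The common level, log AST + log ALT, has no coefficient. The SAP names the untransformed ratio, which is a function of the same difference and is just as blind to k.

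**3. How much level information the log ratio retains.** Let s and t be the SDs of log AST and log ALT, and r their correlation. Define level as the mean of the two logs. The share of variance in level explained by the log ratio is

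R² = (s² − t²)² / [(s² + t²)² − 4r²s²t²].

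The documents give none of these inputs, so a range is shown.

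- Equal SDs (s = t): the numerator is 0, so R² = 0 for any r below 1.
- s = 1.5t: R² = (2.25 − 1)² / [(2.25 + 1)² − 4 × 2.25 × r²] = 1.5625 / (10.5625 − 9r²).
  - r = 0.5: 1.5625 / 8.3125 = 0.19
  - r = 0.9: 1.5625 / 3.2725 = 0.48

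A simulation of 200,000 log-normal pairs gave the same results: 0% with equal SDs, and 19% and 48% with a 1.5-fold difference. At the artificial limit r = 1 with unequal SDs, R² reaches 1, because the two enzymes then move in lockstep and either one determines the other.

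**4. Stated need against stated variable.** The text before the regression requires liver function. The regression supplies only a quantity from which enzyme level has been removed, and no other predictor in the list is a liver measure.

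**The case against.** The strongest reply is that the documents do not show transaminase level to be a measure of hepatic clearance. The determinant of exposure they explain is *CYP2C19* genotype, which is already in the model. On that view, entering the two enzymes separately does not deliver liver function either. This stands as a limit on what can be promised. It does not defend using the ratio alone: the plan chose these two enzymes as its hepatic measure, and separate terms keep information that the ratio throws away.

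Three stronger readings are tempting, and the documents support none of them.

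- **That hepatic impairment cannot be seen by the model.** The ratio is unchanged only when both enzymes rise by the same factor. Unequal rises shift it, and raised enzymes are not the same thing as impaired function.
- **That participants with raised enzymes will be enrolled, and would be missed as likely to exceed 50 ng/ml.** Inclusion criteria exist but are not listed, so silence on hepatic limits is not evidence that there are none. No text links enzyme level to concentrations above the window.
- **That the primary side-effect results are compromised.** The UKU mixed models carry the same term ("Metabolic syndrome (0=No, 1=Yes), Creatinine clearance, AST/ALT ratio"), but their success criterion is the group-by-visit interaction. With two visits, complete data and a time-constant covariate entered as a main effect, that interaction rests on within-person differences, from which the covariate drops out. The UKU logistic models also carry it, but they are offered as an alternative analysis, and the documents show no route from liver function to side effects other than through concentration, which itself defines the groups.

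**Conclusion.** The point holds for the Secondary outcomes regression. The AST/ALT ratio is its only hepatic term, it cannot detect a proportional rise in both enzymes, and it discards enzyme level. That makes it an inadequate sole representation of the liver function the plan says the model needs.

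The algebra needs no assumptions. The retained share of level information (0% with equal log-SDs; about 19% to 48% with a 1.5-fold difference and correlation 0.5 to 0.9) rests on assumed log-normal enzymes and is illustrative. The effect on prediction error, and the number of participants concerned, cannot be computed: the documents give no sample size, enzyme distribution, effect size or list of eligibility criteria. The finding concerns one predictor in one secondary model, built after all participants have finished. It does not extend to the primary HAM-D analyses, whose covariates do not include the ratio, and no consequence for the UKU mixed models is established.

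**What to change.** In the Secondary outcomes regression, replace the AST/ALT ratio with log AST and log ALT as two separate terms, and state that both come from the baseline sample (V0, or V0+k in the alternative course). Naming the visit matters because Hypothesis 4 is about prediction ahead of therapy. For alternative-course participants, already on escitalopram at entry, the V0+k value is the earliest available but is not a pre-treatment one, and the SAP should say so.

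The two-term form contains the log ratio as the special case of equal and opposite coefficients, so the data can show whether level, ratio or both predict concentration. It does not strictly contain the untransformed ratio the SAP now names, so this is a respecification and not a pure extension. A single average of the two logs is not an adequate substitute: it would discard the ratio instead (20/80 and 40/40 have the same mean log, since 20 × 80 = 40 × 40).

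The cost is one extra degree of freedom and a change of SAP wording. No new data collection is needed. The UKU models need no change on this account.
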